## **6.5. Missing Data and Outliers**

Missing immunogenicity data will not be imputed and will be analyzed as if they were randomly missing. Over the study period, the frequency and percentage of subjects who discontinue from the study will be provided by treatment group. All subjects who discontinue post-randomization will be further described regarding their time to and their reasons for discontinuation. For subjects who discontinue from the study, their data collected before discontinuation will be analyzed under the analysis populations as applicable.

## **6.6. Interim Analyses and Data Monitoring**

### **6.6.1. Interim Analysis**

Interim analyses will be performed after the last subject in the first phase has completed Visit 6 (Day 57) assessments and all the results are available. At the time of the interim analysis, safety results (unblinded to the DSMB only) and immunogenicity results (unblinded at group level only) will aid in the selection of formulations to evaluate in the second phase of the study. The interim report will include Tables 4-5, 8-11, 17, 29, 31, 34, 36, 39-42, 60, 64 and 90-119 as well as Listings 7-9.

### **6.6.2. Data Monitoring**

The PI/designee will be responsible for continuous monitoring of all study subjects' safety. In case of urgent need, subjects will have the means to get in contact with study staff at any time (24 hours per day). The PI/designee will also be available by cell phone 24-hours per day for medical emergencies.

Safety will be monitored routinely throughout the study by the PSRT, which includes the PI/designee and other site investigators, the IVAC Clinical Lead, and the Medical Monitor. The PSRT will be continuously involved in safety monitoring and be available to address any urgent medical queries or safety concerns related to any subject's participation in the study. Data management personnel will ensure that the PSRT receives immediate notification of all reported SAEs and any other predefined AEs (e.g., Grade 3 AEs). The PSRT will convene to review blinded safety data on a weekly basis until D43 of the last subject in each phase, then at least once monthly until the end of the study.

During meetings the PSRT will review blinded safety reports and review any outstanding medical or safety queries from the previous review. The blinded safety reports will contain at a minimum, subject disposition and discontinuations, all new Grade 3 and persistent (beyond 6 days post-IP administration) solicited AEs, and all new unsolicited AEs. Cumulative safety data reports will also be made available continuously for review by PSRT members. In addition, the PSRT will review all major protocol deviations in an expedited manner and all other protocol deviations at least on a monthly basis to assess for any potential safety implications, and will provide guidance in the preparation of corrective action plans. The PSRT may also discuss any other study conduct issues that impact study integrity and subject safety, including but not limited to data quality and critical monitoring findings. The PSRT may refer any safety concerns to the DSMB.

A DSMB, composed of at least three independent members with expertise in vaccine clinical trials, will be convened to provide additional safety oversight. In Phase 1, the DSMB will meet to review unblinded safety data through Day 57 (V6), and on the basis of this review provide a recommendation for advancing to Phase 2 (i.e. the DSMB will indicate whether advancement to Phase 2 is warranted based on the reviewed safety data, and whether specific NDV-HXP-S formulations should not be considered for advancement due to safety concerns).

The DSMB will also meet if a study pause rule is met, or the PSRT elects to implement a study pause. If this occurs, no further enrollment will occur, and no study product will be administered until the DSMB approves lifting the pause based on unblinded review of all safety data accrued during the trial. If the study is permanently terminated, subjects who have already received study product will continue with all scheduled protocol visits and assessments; however, they will not receive any further study product.

DSMB reviews will indicate whether or not safety concerns were identified, and whether the trial should continue without change, be modified, or be terminated. The Sponsor will carefully consider the DSMB recommendations. If the Sponsor does not agree with these recommendations, a meeting will be held between the Sponsor, PI, and DSMB to reach consensus on the appropriate action(s) to take in regard to the trial. However, if attempts to reach consensus fail, the Sponsor's opinion will prevail. In such situations, the Sponsor will inform the MoH and NIHE's EC of the Sponsor's perspective, and any changes to the trial. The PSRT, PI or IVAC Clinical Lead may also seek additional guidance from the DSMB as dictated by the occurrence of certain events that do not warrant a study pause.

## **6.7. Multicenter Studies**

Not applicable, Phase 1 is a single center study.

## **6.8. Multiple Comparisons/Multiplicity**

As the two-stage selection design relies on ranking of GMTs, not testing of differences between candidate groups, no adjustment for multiplicity will be performed.

# **7. STUDY PARTICIPANTS**

## **7.1. Disposition of Participants**

Summaries of subject disposition will be prepared for all subjects, including the number and percent enrolled, screened, randomized, and administered study product ([Table 5](#)), as well as a CONSORT diagram ([Figure 1](#)) describing study participation and discontinuation. The reasons for screen failures and discontinuations will be summarized and listed ([Table 6](#), [Listing 1](#)).

## **7.2. Protocol Deviations**

A summary of subject-specific protocol deviations will be presented by study group in the exposed population. The reasons for the deviation will be also included ([Table 4](#), [Listing 2](#)). Protocol deviation may lead to exclusion from the PP population. The summary of analysis population will be presented by study group and visit ([Table 7](#)).

## 8. SAFETY EVALUATION

### 8.1. Demographic and Other Baseline Characteristics

Baseline demographics and characteristics, including age, height, weight, sex, race, ethnicity, and BMI will be summarized for both the exposed and per protocol populations by treatment group using descriptive statistics (mean, standard deviation, median, 25th and 75th quartiles, minimum and maximum for continuous and rates for categorical). Summary tables will be separated by type of data as continuous and categorical (See [Table 8](#) through [Table 11](#)). A listing of individual demographics will be provided ([Listing 3](#)).

#### 8.1.1. Medical History

Medical history will be tabulated by MedDRA System Organ Class (SOC), Preferred Term (PT) and treatment group ([Table 12](#) through [Table 15](#), [Listing 4](#)).

#### 8.1.2. Concomitant Medications

Using the WHO Drug Dictionary, concomitant medications will be tabulated by anatomical therapeutic chemical (ATC) classification, preferred drug name and treatment group ([Table 120](#)). The vaccination history within the past one year will be summarized ([Table 16](#)). Individual subject listing will be prepared for all concomitant medications ([Listing 6](#)).

### 8.2. Measurements of Visit Compliance and Research Sample Collection

A summary of the number of subjects completing each scheduled visit and the number providing research sample results at each visit will be prepared ([Table 17](#)).

### 8.3. Adverse Events

All safety assessment will take place in the safety analysis population, according to the treatment received. All subject-level percentages (solicited/unsolicited AEs, clinical safety laboratory abnormalities, etc.) will be supplemented with two-sided 95% CIs computed via the Clopper-Pearson method. Individual summaries (denominators for percentages) will be limited to the number of subjects with the appropriate analysis population with the data available for analysis for the given endpoint. Summaries will be provided overall by group and by stage ([Table 39](#), [Table 41](#), [Table 42](#), [Table 60](#), [Table 64](#)).

The non-serious adverse events from combined solicited and unsolicited (excluding serious adverse event) that being reported during the first 28 days after each vaccination will be summarized with the number of subject by vaccination groups. This combined data will be summarized by System Organ Class (SOC) and Preferred Term (PT) also ([Table 39](#) and [Table 40](#)).

#### 8.3.1. Solicited Events and Symptoms

Solicited local and systemic adverse events: Percentages of subjects experiencing each solicited AE within 30 minutes observation period and during the first 7 days after each dose vaccination

will be presented for each symptom ([Table 29](#), [Table 31](#), [Table 34](#), [Table 36](#)). All solicited AEs will also be summarized according to defined severity grading scales ([Table 30](#), [Table 32](#), [Table 35](#), [Table 37](#)). Comparison of solicited AE of different dose levels will be done for overall dose, first dose and second dose of each symptom. Data listings of all solicited AEs will be provided by subject ([Listing 7](#)).

Clinically significant hematological and biochemical measurements: For clinical safety laboratory data collected at screening and 7 days post-first administration of study product (Visit 2, Day 8) and post-second administration of study product (Visit 4, Day 36), individual Hgb, WBC count, Plt, AST, ALT, total bilirubin, and creatinine values will be presented as number of subjects out of range (above and below normal range as appropriate) and tabulated by toxicity grading, relatedness, and study group ([Table 60](#) through [Table 68](#)). In addition, mean percentage changes from baseline (95% CI) will be presented. Plot of laboratory results evaluated both pre, post-first and second vaccination will be presented ([Appendix 2.B.- Figure 2](#) through [Figure 8](#)).

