## 8.6. Clinical Laboratory Evaluations

Screening viral serology assessments for Hepatitis B (HBsAg) and Hepatitis C (HCV Ab) will be described as categorical variables on a demographics table ([Table 28](#)).

Clinical safety laboratory values (serum hematology and chemistry) are collected at screening and 7 days post-vaccination for each dose. They will be summarized for the safety analysis population. Hematology and chemistry results evaluated at screening will be summarized as continuous variables by vaccine groups ([Table 24](#) through [Table 27](#)).

Screening and post-vaccination (Day 8 and Day 36) serum hematology and chemistry will be graded by severity. Grade 2 or higher were automatically considered as clinically significant and reported as AE, while Grade 1 abnormalities were subject to investigator opinion.

Continuous summaries of laboratory parameters (Hgb, WBC count, Plt, AST, ALT, total bilirubin, and creatinine) and the change from baseline will be computed by time point (including unscheduled visits, in chronological order) and treatment group, including mean, standard deviation, median, 1st and 3rd quartiles (IQR) and range, for all observations regardless of abnormality status (see [Table 60](#) through [Table 68](#)). Summaries will also be produced presenting the proportion of each severity grading using the number of subjects that provided a sample as denominator, as well as those considered clinically significant, using the maximum severity for a given subject, where relevant. A summary of safety laboratory abnormalities will be prepared by parameter, severity (by grade and any abnormality), and time point. Fisher's exact 2-tailed test will be used to test the differences in abnormality rates across all groups, by time point for scheduled visits, and overall.

Figures will be prepared for each laboratory parameter using boxplots to describe the distribution of values and changes from baseline across visits, by group, incorporating unique points and/or colors for abnormalities ([Figure 2](#) through [Figure 8](#)).

A listing of all lab results will be prepared, in addition to a listing only for abnormalities, and each will include the parameter, study day (Visit), value, units, change from baseline, LLN/ULN, and abnormality grade ([Listing 9A](#), [Listing 9B](#), Appendix 3).

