**Table 19: Vital Signs Toxicity Grading – Protocol Appendix 2**

Vital Signs a	Mild (Grade 1)	Moderate (Grade 2)	Severe (Grade 3)	Potentially Life Threatening (Grade 4)
Tachycardia – beats per minute	101 – 115	116 – 130	> 130	Hospitalization for arrhythmia
Bradycardia – beats per minuteb	50 – 54	45 – 49	< 45	ER visit or hospitalization for arrhythmia
Hypertension (systolic) – mm Hg	141 – 150	151 – 165	> 165	ER visit or hospitalization for malignant hypertension
Hypertension (diastolic) – mm Hg	91 – 99	100 – 105	> 105	ER visit or hospitalization for malignant hypertension
Hypotension (systolic) – mm Hg	85 – 89	80 – 84	< 80	ER visit or hospitalization for hypotensive shock
Respiratory Rate – breaths per minute	21 – 23	24 – 27	> 27	Intubation

a Subject should be at rest for all vital sign measurements.

b Grade 1 bradycardia or grade 1 tachypnea will not be considered an abnormality for this study, unless judged to be clinically significant by the PI in consultation with the Sponsor.

The grading scales for abnormal vital signs have been derived from *Guidance for Industry, Toxicity Grading Scale for Healthy Adult and Adolescent Volunteers Enrolled in Preventive Vaccine Clinical Trials*, U.S. Department of Health and Human Services, FDA, CBER, September 2007.

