**Table 21: Hematology Toxicity Grading – Protocol Appendix 3**

Hematology	Mild (Grade 1)	Moderate (Grade 2)	Severe (Grade 3)	Potentially Life Threatening (Grade 4)
Hemoglobin [Female] (g/dL)	11.0 – 12.0	9.5 – 10.9	8.0 – 9.4	< 8.0
Hemoglobin [Male] (g/dL)	12.5 – 13.5	10.5 – 12.4	8.5 – 10.4	< 8.5
OR Hemoglobin, change from baseline value (g/dL)	1.0 – 1.5	1.6 – 2.0	2.1 – 5.0	> 5.0
WBC, increased (cell/mm  )	10,800 – 15,000	15,001 – 20,000	20,001 – 25,000	> 25,000
WBC, decreased (cell/mm  )	2,500 – 3,400	1,500 – 2,499	1,000 – 1,499	< 1,000
Platelets, decreased (cell/mm  )	100,000 – <125,000	50,000 – < 100,000	25,000 – < 50,000	< 25,000

Abbreviation: ULN = upper limit of normal range

Note: the laboratory values provided in this table serve as guidelines and are dependent upon institutional normal parameters.

The grading scales for laboratory abnormalities have been derived from *Guidance for Industry, Toxicity Grading Scale for Healthy Adult and Adolescent Volunteers Enrolled in Preventive Vaccine Clinical Trials*, U.S. Department of Health and Human Services, FDA, CBER, September 2007, and the *Division of AIDS (DAIDS) Table for Grading the Severity of Adult and Pediatric Adverse Events* (Version 2.1, July 2017) from the US NIH.

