## Appendix 1.E. Hematology Results

**Table 60: Overall Number of Subjects with Any Abnormal Hematology Results in Safety Analysis Population**

	All (N = 120)	COVIVAC				Placebo (N = 20)
		1 µg (N = 25)	3 µg (N = 25)	10 µg (N = 25)	1 µg + CpG (N = 25)	
Overall, n (%)						
with hemoglobin abnormal result	xx (xx.x%)	xx (xx.x%)	xx (xx.x%)	xx (xx.x%)	xx (xx.x%)	xx (xx.x%)
with WBC abnormal result	xx (xx.x%)	xx (xx.x%)	xx (xx.x%)	xx (xx.x%)	xx (xx.x%)	xx (xx.x%)
with platelet abnormal result	xx (xx.x%)	xx (xx.x%)	xx (xx.x%)	xx (xx.x%)	xx (xx.x%)	xx (xx.x%)
with one or more abnormal result	xx (xx.x%)	xx (xx.x%)	xx (xx.x%)	xx (xx.x%)	xx (xx.x%)	xx (xx.x%)
with no abnormal result	xx (xx.x%)	xx (xx.x%)	xx (xx.x%)	xx (xx.x%)	xx (xx.x%)	xx (xx.x%)
Visit 2 (Day 8)						
with hemoglobin abnormal result						
with WBC abnormal result						
with platelet abnormal result						
with one or more abnormal result						
with no abnormal result						
Visit 4 (Day 36)						
with hemoglobin abnormal result						
with WBC abnormal result						
with platelet abnormal result						
with one or more abnormal result						
with no abnormal result						

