**Table 62: White Blood Cell Count Value at each Follow-up Visit Compared to Baseline (continued)**

WBC (x 10  /µL)	All (N = 120)	COVIVAC				Placebo (N = 20)		
		1 µg (N = 25)	3 µg (N = 25)	10 µg (N = 25)	1 µg + CpG (N = 25)			
Change between Day 8 and Baseline								
Mean of % Difference (95% CI)								
Visit 4 (Day 36)								
n								
Mean (SD)								
Median (q1-q3)								
Min-Max								
*p-value =								
Normal								
Abnormal								
Mild								
Moderate								
Severe								
Potentially life threatening								
**p-value=								
Change between Day 36 and Baseline								
Mean of % Difference (95% CI)								

**Note:** + CpG1018 1.5 mg (Adjuvant)

\* P-value based on paired t test/ Wilcoxon signed-rank test

\*\* P-value based on Mc Nemar chi-square test, Normality of results (Normal/Abnormal) will be tested significant difference.

A significance test comparing a baseline (pre-vaccination) with a follow up measurement separately in vaccination group.

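### White-cell counts: Section 8.3.1 promises numbers above and below range, but Tables 60 and 62 give one undirected abnormal category

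*SAP*

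**What the plan says.** Section 8.3.1, laboratory paragraph, covers hemoglobin, WBC, platelets, AST, ALT, total bilirubin and creatinine. It says that "values will be presented as number of subjects out of range (above and below normal range as appropriate", tabulated by toxicity grade, relatedness and group in Tables 60 to 68.

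Table 21 grades "WBC, increased" and "WBC, decreased" on separate four-grade scales. WBC is the only laboratory parameter in Tables 20 and 21 with both.

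Table 60 counts WBC abnormality in one row, "with WBC abnormal result", overall and at Days 8 and 36. Table 62 has, at each visit, one Normal/Abnormal split and one set of grade rows. The key beneath it still lists increased and decreased separately. Its note reads "P-value based on Mc Nemar chi-square test, Normality of results (Normal/Abnormal) will be tested significant difference".

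Section 8.6 adds that Fisher's "exact 2-tailed test will be used to test the differences in abnormality rates across all groups". It lists the dimensions of the abnormality summary as parameter, severity and time point; direction is not among them.

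**The concern.** A raised and a lowered white-cell count are different safety findings, and the SAP's own grading treats them so. Once they share a row, an arm with several low counts can show the same abnormal rate as an arm with several high counts. Where there is some background of high counts in every arm, a real excess of low counts stands out less.

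What is at stake is the readability of a primary safety domain. Section 3.2.1 lists clinically significant hematological measurements among the primary endpoints, and Section 4.1 names clinical laboratory results among the down-selection parameters. Section 6.6.1 puts Table 60 in the interim report but not Table 62 or Figure 3. Table 60, in its pooled form, is thus the only table there devoted to hematology results.

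**Working it through.** The SAP states no abnormality rate, power or p-value on this point, so there is no figure to reproduce. The check is a comparison of text with shells, followed by an illustration.

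**Text against shells**

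| Place | Treatment of direction for WBC |
|---|---|
| Section 8.3.1 | Above and below range, as appropriate |
| Table 21 | Two separate scales |
| Table 60 | One undirected row |
| Table 62, body | One Normal/Abnormal block, one set of grades |
| Table 62, key | Two scales |
| Table 62, McNemar note | Pooled status |
| Section 8.6, Fisher | Not stated |

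The qualifier in 8.3.1 has to apply to WBC if it applies anywhere. A programmer who follows the shell must merge the two scales.

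**McNemar test within an arm.** The statistic is (b − c)²/(b + c), where b counts normal-to-abnormal and c abnormal-to-normal.
- A subject who goes from high to low is abnormal both times and enters neither b nor c.
- Suppose three subjects go from high to normal and three from normal to low. All six have fallen, but b = c = 3 and the statistic is (3 − 3)²/6 = 0. Split by direction, each test has 3 discordant subjects, all one way: 3²/3 = 3.

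**Fisher test across the five arms, if it uses the same status.** Arm sizes are 25/25/25/25/20 (Table 1), 120 in all. Assume k low results in one arm of 25, none elsewhere, and about the same rate of high results in each other arm.

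For low results alone, the tables no more probable than the observed one are those with all k in a single arm, so

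p = [4·C(25,k) + C(20,k)] / C(120,k)

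- k = 3: (4 × 2,300 + 1,140)/280,840 = 0.037
- k = 4: (4 × 12,650 + 4,845)/8,214,570 = 0.0067
- k = 5: (4 × 53,130 + 15,504)/190,578,024 = 0.0012
- k = 6: (4 × 177,100 + 38,760)/3,652,745,460 = 0.0002

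The pooled counts are 3/3/3/3/2, 4/4/4/4/3, 5/5/5/5/4 and 6/6/6/6/5. Full enumeration gives p = 1.000 for each. At k = 5 every arm stands at 20% (5/25 and 4/20).

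**Partial dilution, one vaccine arm against placebo (25 vs 20).** This pairwise test is not the SAP's all-group test; it shows only how background matters. Exact power of a two-sided 5% Fisher test for 30% vs 1% low WBC is 74% with low results counted alone. Pooled with background high WBC of 5, 10 or 15%, power depends on how the background is modelled:
- background arising only among subjects without low WBC: 58%, 45%, 37%
- background added as full percentage points in both arms: 62%, 53%, 48%

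**The case against.** The strongest reply is that direction is not lost. Listings 9A and 9B show each value with its reference range, percent change and severity. They are in the interim report, and 120 subjects can be read one by one. Section 8.6 makes Grade 2 or higher an adverse event automatically, so graded rises and falls may appear under different preferred terms in Table 40, which is also in the interim set. In the final report, Table 62 gives means, ranges, percent change and a paired test, and Figure 3 gives box plots. All of this stands. It confines the harm to the abnormal counts, the grade rows and the abnormality tests. Even so, the listings have no high/low column, so the interim reader must work direction out by hand.

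A second reply is that Section 1 calls the shells samples and that 8.3.1 already requires both directions. That supports aligning the shells; it does not make them consistent.

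A third is that the illustrative counts are chosen to offset each other, in adults screened as healthy. That is correct. Complete cancellation is an extreme case; dilution is the general effect.

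A reader might also infer that the vital-sign tables breach 8.3.1, because Table 19 grades "Hypotension (systolic) – mm Hg" apart from systolic hypertension, and bradycardia apart from tachycardia, while Tables 69 to 72 and 75 to 76 pool them. The documents do not support that. The sentence in 8.3.1 covers laboratory values only, and Section 8.7 makes no above/below promise. For pulse, Grade 1 bradycardia is by default not counted as abnormal, which limits the pooling further.

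**Conclusion.** The inconsistency is real and concerns one laboratory parameter. Section 8.3.1 and Table 21 separate WBC by direction; Tables 60 and 62 do not, and the McNemar test explicitly runs on the pooled status. Whether the Fisher test does so too is an inference, since Section 8.6 does not define its input and neither shell carries a Fisher p-value line.

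The effect is a less informative count and a weaker abnormality test. It would go too far to conclude that a fall in WBC would escape the safety assessment, given the listings, adverse-event tables and continuous summaries. Nor does the SAP make a laboratory p-value decide down-selection: Section 4.1 has the DSMB review unblinded safety data.

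All p-values and powers above rest on assumed rates and show the mechanism only. The point is modest but worth correcting, because Table 60 is the interim report's only hematology results table.

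**What to change.** In Tables 60 and 62, replace the single WBC abnormal and grade rows with two sets, WBC increased and WBC decreased, each graded as in Table 21. Run the McNemar test separately for each direction, and state in Section 8.6 that the Fisher test for WBC is also run by direction.

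As an optional extension for consistency with Table 19, split systolic pressure (hypertension, hypotension) and pulse (tachycardia, bradycardia) in the same way in Tables 69 to 72 and 75 to 76.

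The cost is a few rows in existing shells and no new data. The downside is more tests on small counts, so the split p-values should be read as descriptive.

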## 8.7. Vital Signs and Physical Evaluations

Vital sign measurements including systolic and diastolic blood pressure (mmHg), temperature (°C), pulse (beats/min) and respiratory rate (breaths/minute) will be assessed at each visit, including change from pre-first vaccination and pre-second vaccination ([Table 69](#) through [Table 80](#)). Vital signs will be tabulated by visit and vaccination group, including mean, standard deviation, median and range. A full listing will be prepared ([Listing 10](#), Appendix 3) and will include study visit, value, units and change from baseline.

Physical exam results, including number and proportion of participants with abnormalities, will be summarized for the safety analysis population and presented in [Appendix 1.H. \(Table 81](#) through [Table 89\)](#), by vaccination group. A full listing will be prepared ([Listing 12](#), Appendix 3).

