**Table 66: ALT Value at each Follow-up Visit Compared to Baseline in Safety Analysis Population (continue)**

ALT (U/L)	All (N = 120)	COVIVAC				Placebo (N = 20)		
		1 µg (N = 25)	3 µg (N = 25)	10 µg (N = 25)	1 µg + CpG (N = 25)			
Change between Day 8 and Baseline								
Mean of % Difference (95% CI)								
Visit 4 (Day 36)								
n								
Mean (SD)								
Median (q1-q3)								
Min-Max								
*p-value =								
Normal								
Abnormal								
Mild								
Moderate								
Severe								
Potentially life threatening								
Change between Day 8 and Baseline								
Mean of % Difference (95% CI)								

**Note:** + CpG1018 1.5 mg (Adjuvant)

\* P-value based on Kruskal Wallis Test

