**Listing 9A: All Clinical Laboratory Values**

Subject ID	Vaccination Group	Parameter	Units	Reference Range	Visit	Value	% Change from Baseline	Severity
		Hemoglobin	g/dL		Baseline			
					Visit 2 (Day 8)			
					Visit 4 (Day 36)			
		White Blood Cell	$\times 10^3/\mu\text{L}$		Baseline			
					Visit 2 (Day 8)			
					Visit 4 (Day 36)			
		Platelets	$\times 10^3/\mu\text{L}$		Baseline			
					Visit 2 (Day 8)			
					Visit 4 (Day 36)			
		Creatinine	mg/dL		Baseline			
					Visit 2 (Day 8)			
					Visit 4 (Day 36)			
		AST (SGPT)	U/L		Baseline			
					Visit 2 (Day 8)			
					Visit 4 (Day 36)			
		ALT (SGOT)	U/L		Baseline			
					Visit 2 (Day 8)			
					Visit 4 (Day 36)			
		Total Bilirubin	mg/dL		Baseline			
					Visit 2 (Day 8)			
					Visit 4 (Day 36)			

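### The laboratory and vital-sign table shells give change only as a mean percent difference, whereas Sections 8.6 and 8.7 promise plain change; that mean is biased upward for variable analytes and depends on the unit for temperature

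*SAP*

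**What the plan says.** Section 8.6 (Clinical Laboratory Evaluations) plans continuous summaries of each laboratory parameter "and the change from baseline will be computed by time point (including unscheduled visits, in chronological order) and treatment group". It specifies mean, standard deviation, median, quartiles and range, and points to Tables 60 to 68. For the laboratory listings it says that "each will include the parameter, study day (Visit), value, units, change from baseline", among other items.

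Section 8.7 plans vital-sign assessment at each visit, "including change from pre-first vaccination and pre-second vaccination", and points to Tables 69 to 80.

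Section 8.3.1, after the counts of out-of-range values and the toxicity grading, has one further sentence for laboratory values, worded as an addition: "mean percentage changes from baseline (95% CI) will be presented".

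The shells differ. In Tables 61-63 (haematology), 65-68 (chemistry) and 71-80 (vital signs, including temperature) the only change statistic is the row "Mean of % Difference (95% CI". No shell has a row for plain change, or for the SD, median, quartiles or range of any change. In Listings 9A and 9B the column "Change from Baseline" carries a percent sign in front. Listing 10 (vital signs) gives plain change, as Section 8.7 asks.

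**The concern.** There are two separate faults.

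First, someone programming from the shells would leave out the summaries that Sections 8.6 and 8.7 promise, and would report percent change for vital signs, which no text requests.

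Second, the one statistic left is a poor one for reading change within an arm. Each percent change is divided by a single noisy baseline, and low baselines inflate the ratio more than high baselines shrink it. The arithmetic mean is therefore pushed upward with no vaccine effect. In a first-in-human study a reader is likely to check whether the CI in an arm excludes zero, and for variable analytes it will do so on the upper side too often. For temperature, whose zero is arbitrary, a percentage has no fixed meaning.

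**Working it through.** The SAP states no figure on this point, so there is none to reproduce.

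**Step 1: text against shells.**

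| Output | Text asks for | Shell provides |
|---|---|---|
| Tables 61-63, 65-68 | Plain change with mean, SD, median, quartiles, range (8.6); mean percent change with CI in addition (8.3.1) | Mean percent difference with CI only |
| Tables 71-80 | Change from the pre-dose value (8.7) | Mean percent difference with CI only |
| Listings 9A, 9B | Change (8.6) | Percent change |
| Listing 10 | Change (8.7) | Change |

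**Step 2: direction of the bias.** Let X be the baseline and Y the follow-up value, exchangeable because nothing has changed. Then E[Y/X] = E[X/Y]. For any positive ratio r, (r + 1/r)/2 ≥ 1. Hence E[Y/X] ≥ 1, and the expected percent change is at least zero, strictly above it once there is within-person variation. No distributional form is needed. Example: ALT going 20→40 U/L in one subject and 40→20 U/L in another has mean plain change (20 − 20)/2 = 0 but mean percent change (100% − 50%)/2 = +25%.

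**Step 3: size.** Assume independent lognormal within-person errors with coefficient of variation CV, so the log-scale variance per measurement is s² = ln(1 + CV²). Then log(Y/X) has mean 0 and variance 2s², so E[Y/X] − 1 = exp(s²) − 1 = CV². The SAP gives no within-person CV, so a range is shown. The arm size of 25 is from Section 5. The CI column is simulated (40,000 runs, t interval on the mean percent change).

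| Assumed CV | Expected mean percent change, no effect | 95% CI wholly above zero, n = 25 (nominal 2.5%) |
|---|---|---|
| 5% | 0.05² = +0.25% | about 3% |
| 10% | 0.10² = +1.0% | about 4% |
| 20% | 0.20² = +4.0% | about 6.5% |
| 30% | 0.30² = +9.0% | about 10% |

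Under the same model the intervals for mean plain change and for the mean log ratio lie above zero in roughly 2.2% to 2.5% of arms at these CVs. In the pooled column of 120 subjects the percent-change interval lies above zero in about 5.5%, 11%, 29% and 54% of runs, because the bias stays fixed while the interval narrows.

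**Step 4: temperature.** A rise from 37.0 to 38.5 °C is 1.5/37.0 = 4.05%. The same rise in Fahrenheit is 98.6 to 101.3 °F, or 2.7/98.6 = 2.74%. As plain change it is +1.5 °C.

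**The case against.** The shells are not bare. Each prints n, mean, SD, median, quartiles and range at every visit, with normal/abnormal counts and grades. With complete pairs, the mean plain change is the difference of two printed means. Tables 61-63 and 71-80 add a paired t or Wilcoxon test, ordinarily run on the measured values, and Tables 65-68 a Kruskal-Wallis test. Section 8.6 also plans boxplots of changes from baseline. All this is right, but the SD, median, quartiles and CI of a paired change cannot be recovered from visit-wise summaries, so the promised statistics are still missing from the tables.

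The size rests on an assumed CV. At 5% the bias is negligible, and the SAP does not show which analytes exceed that. This stands, and it limits the bias argument to the more variable ones.

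Three stronger readings are tempting and should not be drawn:

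- **That Section 8.3.1 contradicts Section 8.6.** It does not; it offers percent change as a supplement. The conflict is between the text and the shells.
- **That every arm would show a spurious rise.** Under the same model, at CVs of 20% to 30%, the mean percent change is positive in about 75% to 83% of arms of 25, and in all five arms together in only about 22% to 38% of trials. Some 90% or more of arm-level intervals would not lie above zero. The placebo column carries a similar bias and so helps to expose it.
- **That formulation selection would be distorted.** The interim report listed in Section 6.6.1 takes Tables 60 and 64 (abnormality counts) and Listings 7-9, but none of Tables 61-63, 65-68 or 71-80.

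On temperature, the shell titles fix the unit as °C, so arms are compared on one scale. The objection is to the meaning of the percentage; it does not bias the comparison.

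**Conclusion.** The mismatch is established from the document alone: the plain change promised in Sections 8.6 and 8.7 has no row in Tables 61-63, 65-68 or 71-80, percent change for vital signs has no basis in the text, and Listings 9A and 9B depart from Section 8.6.

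The upward bias of the mean percent change is also established in direction, needing only exchangeability of baseline and follow-up under no effect. Its size depends on within-person variation that the SAP does not give: immaterial near a CV of 5%, material from about 20%. It acts on within-arm intervals read against zero; contrasts with placebo are much less affected. For temperature the percentage is not interpretable.

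This should be put right before programming, but it does not threaten the safety grading or the decision to advance a formulation.

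**What to change.** 1. In Tables 61-63, 65-68 and 71-80, add rows for plain change at each follow-up visit: mean, SD, median, quartiles and range, with a 95% CI for the mean. The CI goes beyond Sections 8.6 and 8.7, neither of which specifies one for change, so add it to both.
2. Remove the percent-difference row from the vital-sign tables (71-80).
3. If a relative change is kept for laboratory values under Section 8.3.1, report the back-transformed mean log ratio to baseline with a t-based CI in Tables 61-63 and 65-68, instead of the mean of individual percent changes, and reword the sentence in 8.3.1 to match. Section 9 already uses this method for the geometric mean fold rise. It supplements the plain-change rows and does not replace them; otherwise the laboratory tables would still fall short of Section 8.6.
4. Add a plain-change column to Listings 9A and 9B.

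While these rows are open, correct the label of the second change row in Tables 65-68, which repeats Day 8 after the Day 36 visit.

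The cost is SAP wording, shell edits and minor programming on data already collected.
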